10.2.1.1 Haematology

Haemoglobin, haematocrit, red blood cell count, white blood cell count with differential (neutrophils, lymphocytes, monocytes, basophils, eosinophils), platelet count, mean corpuscular haemoglobin, mean corpuscular volume, mean corpuscular haemoglobin concentration

10.2.1.2 Clinical chemistry

Glucose, sodium, potassium, chloride, bicarbonate, calcium (corrected), creatinine, urea, uric acid, amylase, lipase, triglyceride, HDL-cholesterol, LDL-cholesterol, total cholesterol, total protein, lactate dehydrogenase, creatine kinase, C-reactive protein, albumin, phosphate. HbA1c will be measured in DPN subjects only and only at screening.

Aspartate aminotransferase, alanine aminotransferase, gamma-glutamyl transferase, alkaline phosphatase, conjugated bilirubin, total bilirubin

Activated partial thromboplastin time, international normalised ratio

10.2.1.3 Urinalysis

Specific gravity, pH, glucose, protein, blood, ketones, urobilinogen, bilirubin, nitrite, leukocytes.

If urinalysis on dipstick is positive for leukocytes and/or blood/haemoglobin, a microscopic examination including erythrocytes, leucocytes, bacteria, casts, epithelial cells and crystals will be performed.

10.2.1.4 Pregnancy

Human chorionic gonadotropin levels (hCG) will be measured in blood samples from females of child-bearing potential at screening. Urine hCG will be measured on Day 1.

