2.1 Screening, First Baseline Period, First Treatment Period and Washout

	Screening	Screening Stage 2 (First					
	Stage 1 Baseline)		Firs	t Treatment Pe	eriod	Washout	
Visit No	1		2 3 4		4		
Study Day	-28 to -8	-7 to -1	1	14 ± 1	28 ± 1	29 (+/-1) to 42 (+/-1)	
Written informed consent	Х						
Eligibility assessment	Х						
Pain diary training	Х						
Confirmation of eligibility			Х				
Enrolment			Х				
Randomisation			Х				
Medical history, demographics	Х						
Height, ¹ weight	Х		Х	Х	Х		
PD-Q	Х		Χ				
12 lead ECG	Х		X ²		X ²		
Vital signs	Х		X^3	Х	Х		
Physical examination ⁴	Х		X ⁵	X ⁵	X ⁵		
Concomitant medications	Х		Χ	Х	Х		
Clinical laboratory safety testing ⁶	Х		X ^{2,7}		X ²		
Pregnancy test ⁸	X ⁹		X ¹⁰				
QST sensory phenotype assessment ¹¹			X ¹²		Х		
IMP administration			X ¹³	Х	X ¹³		
Adverse event assessment	X ¹⁴	X ¹⁴	Χ	Х	Х		
Blood sampling for PK analysis ¹⁵			X ¹⁶		X ¹⁶		
Daily NPRS ratings ¹⁷		Х	X ¹⁸	Х	X ¹⁸	Х	
Short form BPI assessment			Х		Х		
Short form McGill questionnaire 2			Χ		Х		
Neuropathic Pain Symptom Inventory			Χ		Х		
Beck Depression Index-II			Χ		Х		
PGIC					Х		

- 1 Height measured only at screening
- 2 Pre-dose
- 3 Pre-dose and 0.5 hours post-dose
- 4 Includes assessment of area of pain
- 5 Targeted physical examination
- 6 Haematology, clinical chemistry, urinalysis
- 7 Results of clinical laboratory tests not required prior to dosing
- 8 Females of child bearing potential only
- 9 Blood pregnancy test
- 10 Urine pregnancy test
- 11 QST subjects only
- 12 QST to be assessed pre-dose, within 7 days of the first dose
- 13 Supervised administration
- 14 SAEs only (UK subjects only)
- 15 PK subjects only
- 16 Pre-dose and up to 6 hours post-dose
- 17 Each evening, throughout baseline, treatment and washout periods
- 18 Additional ratings pre-dose and up to 6 hours post-dose in PK subjects

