2.2 Second Baseline Period, Second Treatment Period and Follow Up

	Second Baseline Period	Second Treatment Period			End of Study
Visit No		5	6	7	8
Study Day	43 to 49	50 ± 1	63 ± 1	77 ± 1	91 ± 2
Weight		Х	Х	Х	Х
12 lead ECG		X ¹⁹		X ¹⁹	
Vital signs		X ²⁰	Х	Х	Х
Physical examination ²¹		X ²²	X ²²	X ²²	X ²²
Concomitant medications		Х	Х	Х	Х
Clinical laboratory safety testing ²³		X ^{19,24}		X ¹⁹	Х
QST sensory phenotype assessment ²⁵		X ²⁶		Х	
IMP administration		X ²⁷	Х	X ²⁷	
Adverse event assessment		Х	Х	Х	Х
Blood sampling for PK analysis ²⁸		X ²⁹		X ²⁹	
Daily NPRS ratings ³⁰	Х	X ³¹	Х	X ³¹	
Short form BPI assessment		Х		Х	
Short form McGill questionnaire 2		Х		Х	
Neuropathic Pain Symptom Inventory		Х		Х	
Beck Depression Index-II		Х		Х	
PGIC				Х	

¹⁹ Pre-dose

²⁰ Pre-dose and 0.5 hours post-dose

²¹ Includes assessment of area of pain

²² Targeted physical examination

²³ Haematology, clinical chemistry, urinalysis

²⁴ Results of clinical laboratory tests not required prior to dosing

²⁵ QST subjects only

²⁶ QST to be assessed pre-dose, within 7 days of the first dose of this treatment period

²⁷ Supervised administration

²⁸ PK subjects only

²⁹ Pre-dose and up to 6 hours post-dose

³⁰ Each evening throughout baseline and treatment periods

³¹ Additional ratings pre-dose and up to 6 hours post-dose in PK subjects

3. Introduction and background information

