On Day 50, subjects will return to the clinic and cross over to receive the second treatment (either LAT8881 or placebo, whichever treatment was not received in the first treatment period) twice daily for four weeks (Days 50 to 77). On the morning of Day 77, they will return to the clinic for their end of second treatment visit and will take an IMP capsule in the morning during their clinic visit. They will take their final IMP dose for this treatment period in the evening.

Subjects will return to the clinic on Day 91, two weeks after their last treatment visit, for an end of study visit.

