6.1 Inclusion criteria

Subjects must meet the following criteria to be entered into the study:

1. Clinical diagnosis of post herpetic neuralgia, with pain persisting for at least 3 months after the onset of herpes zoster rash

OR

- 2. Clinical diagnosis of distal painful polyneuropathy due to Type I or Type II diabetes mellitus with:
 - a) symmetrical, bilateral pain in the lower extremities for at least 3 months and
 - b) diabetes under control for at least 3 months prior to randomisation, as indicated by a glycated haemoglobin level (HbA1c) of ≤ 11% (97 mmol/mol) and on a stable dose of insulin or oral diabetic medication for 3 months prior to screening, and
 - c) no change in diabetic medication planned for the duration of the study
- Positive sensory symptoms (mechanical or thermal) associated with neuropathic pain, confirmed by:
 - a) painDETECT Questionnaire (PD-Q) and
 - b) Clinical assessment, showing signs of neuropathic pain in either a dermatomal (PHN) or distal symmetrical distribution (DPN)
- 4. Aged 18 to 75 years
- 5. Subjects must be sufficiently competent in English to understand the purposes and risks of the study and able to give voluntary written informed consent to participate in the study
- 6. Willing and able to comply with all study procedures
- 7. Completion of at least five NPRS scores during the week preceding randomisation
- 8. An average daily pain score on the NPRS of at least 4 and no more than 8 in the last five diary entries before randomisation
- 9. No more than one score on the NPRS of 9 or more, and no more than one score of 2 or less, in the last five diary entries before randomisation
- 10. Females of child bearing potential must have a negative pregnancy test at Visit 1 (Screening) and at Visit 2 (Day 1) prior to administration of IMP
- 11. Female subjects must be:
 - a) of non child-bearing potential [surgically sterilised or post–menopausal (12 months with no menses without alternative medical cause)] OR
 - not pregnant, breast feeding or planning to become pregnant AND willing to comply with the medically acceptable contraceptive requirements of the study from Screening to at least 28 days after the last IMP administration

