8.2.2 Screening Stage 2 (first baseline)

Subjects deemed likely to be eligible for the trial will record their pain assessments each evening in their diary.

8.3 First treatment period (Days 1 to 28), Visits 2 to 4

8.3.1 Day 1, Visit 2

Subjects will return to the unit on Day 1 (Visit 2) with their diary completed from Days -7 to -1 inclusive.

The following assessments will be undertaken on Day 1:

- Review of the subject's pain diary
- Weight
- PD-Q
- ECG
- Vital signs
- Targeted physical examination, including assessment of painful regions
- Concomitant medications
- Blood sample for routine haematology and clinical chemistry assessments
- Urine sample for urinalysis (dipstick) and, in female subjects of child-bearing potential, a urine sample for pregnancy testing

Results from safety monitoring tests are not required prior to dosing. Eligible subjects will be enrolled, assigned a unique Randomisation Number and randomised to LAT8881 or placebo.

Subjects will complete baseline assessments for Patient Reported Outcomes:

- Interference scale of the short form BPI
- SF-MPQ-2
- NPSI
- BDI-II

In PK subjects, a pre-dose NPRS will be completed (maximum one hour before dosing) and a pre-dose blood sample taken for PK analysis. QST subjects will have a pre-dose QST assessment, if not completed within the previous 7 days.

Subjects (except for PK subjects) will take their first dose of IMP and remain in the clinic for up to one hour to check for any adverse events. Vital signs will be measured 30 (+/-10) minutes after IMP dosing.

PK subjects will take their first dose of IMP and remain in the clinic for at least 6 hours. At scheduled times (2, 5, 15, 30, 60 minutes, 2, 4 and 6 hours after IMP dosing), blood samples will be taken for PK analysis. NPRS will be monitored at 0.5, 1, 2, 4 and 6 hours. Vital signs will be measured 30 (+/-10) minutes after IMP dosing.

Before leaving the clinic, each subject will be reminded to take a dose of IMP twice daily and to continue recording pain scores in their diary each evening.

All subjects will leave the unit with sufficient IMP for the first treatment period.

8.3.2 Day 14 (± 1), Visit 3

On Day 14 (Visit 3), subjects will take their morning IMP dose and return to the clinic with their medication bottle. The following assessments will be undertaken:

- Weight
- Vital signs
- Targeted physical examination
- Concomitant medications
- Adverse events
- Compliance with medication
- Compliance with diary entries

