8.5 Second baseline period (Days 43-49)

During the second baseline period (Days 43 to 49 inclusive), subjects will continue their diary entries and will not take any IMP. They will record their NPRS rating each evening.

8.6 Second treatment period (Days 50-77), Visits 5 to 7

Subjects will return to the unit on Day 50 (± 1) with their diary completed from Days 29 to 49 inclusive and with their medication bottle.

8.6.1 Day 50 (± 1), Visit 5

Subjects will return on Day 50, and the following assessments will be undertaken:

- Review of the subject's pain diary (Days 43-49 inclusive)
- Weight
- ECG
- Vital signs
- Targeted physical examination, including assessment of area of pain
- · Concomitant medications
- Blood and urine samples for safety analysis (haematology, clinical chemistry, urinalysis)

Results from safety monitoring tests are not required prior to dosing. Subjects will also complete their second baseline assessments for Patient Reported Outcomes:

- Interference scale of short form BPI
- SF-MPQ-2
- NPSI
- BDI-II

In PK subjects, a pre-dose NPRS will be completed (maximum one hour before dosing) and a pre-dose blood sample taken for PK analysis. QST subjects will have a pre-dose QST assessment, if not completed within the previous 7 days.

Subjects (except for PK subjects) will take their allocated IMP and will remain in the clinic for up to one

hour to check for adverse events. Vital signs will be measured 30 (+/-10) minutes after IMP dosing.

PK subjects will take their allocated IMP and will remain in the clinic for at least 6 hours. At scheduled times (2, 5, 15, 30, 60 minutes, 2, 4 and 6 hours after IMP dosing), blood samples will be taken for PK analysis. NPRS will be monitored at 0.5, 1, 2, 4 and 6 hours. Vital signs will be measured 30 (+/-10) minutes after IMP dosing.

All subjects will leave the unit with sufficient IMP for the second treatment period. They will be reminded to complete their NPRS diary each evening.

8.6.2 Day 63 (± 1), Visit 6

On Day 63 (Visit 6), subjects will take their morning IMP dose and return to the clinic with their medication bottle. The following assessments will be undertaken:

- Weight
- Vital signs
- Targeted physical examination
- Concomitant medications
- Adverse events
- Compliance with medication
- Compliance with diary entries

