10.2 Treatment

The following treatment variables along with corresponding numeric equivalents will be included as core variables in all analysis datasets:

- Planned / Actual Treatment Sequence : LAT8881 60 mg-Placebo, Placebo-LAT8881 60 mg •

Planned / Actual Treatment: LAT8881 60 mg, Placebo

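### No pregnancy test is scheduled before the second treatment starts on Day 50, so women in the placebo-LAT8881 sequence take their first LAT8881 dose 49 days after their last test

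*Protocol*

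**What the plan says.** - **Entry rule.** Under inclusion criterion 10 (Protocol Section 6.1), women of child-bearing potential "must have a negative pregnancy test at Visit 1 (Screening) and at Visit 2 (Day 1) prior to administration of IMP".
- **First period.** The Day 1 visit list (Section 8.3.1) includes, "in female subjects of child-bearing potential, a urine sample for pregnancy testing". The Section 2.1 schedule has a pregnancy-test row marked at screening and on Day 1, and the Day 1 footnote reads "Urine pregnancy test". Section 10.2.1.4 agrees: blood hCG at screening, and "Urine hCG will be measured on Day 1".
- **Second period.** The Section 2.2 schedule has no pregnancy-test row. The Day 50 list (Section 8.6.1) names "Blood and urine samples for safety analysis (haematology, clinical chemistry, urinalysis". The urinalysis analytes in Section 10.2.1.3 do not include hCG. The Day 50 laboratory samples are marked pre-dose, with the footnote "Results of clinical laboratory tests not required prior to dosing".
- **Crossover.** On Day 50 subjects "cross over to receive the second treatment (either LAT8881 or placebo, whichever treatment was not received in the first treatment period" (Section 5.1). The SAP names the sequences as "LAT8881 60 mg-Placebo, Placebo-LAT8881 60 mg" (Section 10.2).
- **SAP.** The second-period schedule (Section 5.2) has no pregnancy test, and the listing in Section 11.7.2.3 covers Screening and Day 1 only.

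**The concern.** In the placebo-LAT8881 sequence, Day 50 is the first exposure to LAT8881. A woman of child-bearing potential in that sequence receives it on the strength of a test seven weeks old, her contraception and her own report. A pregnancy that began during the first treatment period or early in the washout could be exposed to LAT8881, although a test on urine collected that morning might have shown it.

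Nothing else in the plan checks for pregnancy at that point. Adverse-event questioning (Section 10.3) helps only if she already suspects it. The reporting duty in Section 12.4 begins once a pregnancy is known. The discontinuation reasons in Section 5.7 and the stopping criterion in Section 11.1 do not name pregnancy.

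**Working it through.** **Is the test really absent?** The protocol schedule, the Day 50 visit list, the laboratory section and both SAP locations agree that there is no test after Day 1. This is therefore neither a redaction nor a broken table.

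**Time from last test to LAT8881.** The plan states no figure to reproduce, so this is day arithmetic.

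- Inputs: last test on Day 1 (Section 10.2.1.4); second treatment starts on Day 50 ± 1 (Section 8.6.1); active dosing on Days 1–28 or Days 50–77 (Section 5.1).
- Placebo-LAT8881, first active dose: 50 − 1 = 49 days. With the window, 49 − 1 = 48 to 51 − 1 = 50 days. Cross-check: 28 treatment days + 14 washout days + 7 second-baseline days = 49.
- Placebo-LAT8881, last day of active dosing: 77 − 1 = 76 days after the test.
- LAT8881-placebo: first active dose 1 − 1 = 0 days after the test, last 28 − 1 = 27 days.
- With a test on Day 50, active dosing in the placebo-LAT8881 sequence would run from 50 − 50 = 0 to 77 − 50 = 27 days after the latest test, matching the other sequence.

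**Expected number of pregnancies.** The documents do not give the number of women of child-bearing potential. Section 6.3 requires a failure rate below 1% but states no time base. Assumptions: N = 5 to 20 such women among the 55 planned, half of them in the placebo-LAT8881 sequence, and failure at 1% per year.

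Expected pregnancies beginning between Day 1 and the first active dose = (N/2) × 0.01 × 49/365:

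- N = 5: 2.5 × 0.01 × 49/365 = 0.0034
- N = 20: 10 × 0.01 × 49/365 = 0.0134

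The upper value is about one pregnancy in 1/0.0134 ≈ 75 trials of this size. As an extreme reading of the missing time base, the whole 1% could be placed in these 49 days. That gives 2.5 × 0.01 = 0.025 to 10 × 0.01 = 0.10, still well below one event.

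**How much would a Day 50 test catch?** It is tempting to subtract conceptions too recent to show on Day 50. The same detection lag L applies to the Day 1 test, however. A Day 50 test adds conceptions from L days before Day 1 to L days before Day 50, which is again a 49-day span whatever L is. At a constant rate the count stays at about 0.003 to 0.013. The rate may not be constant, because the earliest part of that span falls before Day 1, when required contraception had been in place for less time.

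**The case against.** **No rule is broken, and this stands.** A reader might infer that the protocol sets a same-day negative test before the first active dose and then fails to apply it in one sequence. The documents do not say that. Criterion 10 concerns entry and IMP, and the synopsis defines IMP as LAT8881 or placebo. Both sequences meet it in the same way, and the protocol and SAP do not conflict. A Day 50 test would be an added safeguard.

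**Day 1 and Day 50 differ, and this stands too.** A reader might argue that contraception and adverse-event questioning applied equally on Day 1, so that requiring a test then and omitting it on Day 50 is inconsistent. They did not apply equally. Contraception is required from screening, and Screening Stage 1 runs from Day −28 to Day −8. By Day 1 it has been in force for 8 to 28 days; by Day 50, for at least 8 + 49 = 57 days. She has also been questioned about adverse events at the Day 14 and Day 28 visits. The Day 1 test can pick up a conception that predates the contraception requirement, a purpose that Day 50 largely lacks.

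**The risk is low, and this stands.** The count above already allows for contraception. Section 3.2.1.2 reports no effect on reproduction in rats at up to 100 mg/kg/day, no effect on foetal development in rabbits at up to 50 mg/kg/day, and considers a genotoxic hazard unlikely. Known pregnancies are reported on the 24-hour SAE timeline.

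These arguments settle how much weight the point can bear. They do not supply a check before the Day 50 dose or a reason for leaving one out.

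**Conclusion.** The gap is real and verified: 49 days (48 to 50) from last test to first LAT8881 dose in one sequence, against 0 in the other. It is a design choice worth improving, not an error or a breach. The expected count of 0.003 to 0.013 pregnancies rests on an assumed 5 to 20 women, equal allocation and 1% failure per year, and it scales in proportion to the number of women and the failure rate. A same-day test is not complete protection in either sequence, since very recent conceptions would be missed on Day 1 or Day 50 alike. Efficacy, power and sample size are untouched. The case rests on giving both sequences a current test before active drug at little cost, not on the number of events to be prevented.

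**What to change.** In all women of child-bearing potential, run the urine hCG test used on Day 1 on the pre-dose urine already collected at Visit 5 (Day 50). It has to be all such women because sites are blinded to sequence (Section 7.6). Require a negative result before dosing, and write this as an explicit exception to the Day 50 statement in Section 8.6.1 and its schedule footnote, "Results of clinical laboratory tests not required prior to dosing". If the result is positive, give no dose and complete a Pregnancy Report Form under Section 12.4. Update Protocol Sections 2.2, 8.6.1 and 10.2.1.4, and add Day 50 to the pregnancy listing in SAP Section 11.7.2.3.

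The main cost is the amendment. Under Section 14.1.4 it needs ethics committee approval, UK regulator approval if substantial, and approval of revised subject information if that changes. Beyond that there is one urine test per eligible woman and a short wait before the Day 50 dose. No extra visit or sample is needed, and sites already perform dipstick urinalysis (Section 10.2.1) and must already have the Day 1 pregnancy result before dosing.

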10.2.2 Pharmacokinetics

Blood samples (4 mL) will be taken pre-dose (within 30 minutes of dosing) and 2, 5, 15, 30, 60 minutes, 2, 4 and 6 hours after IMP ingestion. Blood samples will be obtained by direct venepuncture or via an indwelling cannula. Samples taken 2, 5 and 15 minutes after dosing should be within +/- 1 minute of the stated time, samples at later time points within +/- 5 minutes of the stated time.

Blood samples

will be kept on ice immediately after collection to minimise degradation and centrifuged within 60 minutes post-collection in a pre-cooled (refrigerated) centrifuge. The resulting PK plasma samples will be transferred to clean, pre-labelled polypropylene tubes and stored frozen prior to analysis. Pre-dose samples will be centrifuged separately prior to dosing.

Further details will be provided in the Laboratory Manual.

Samples will be analysed under GLP conditions by

An initial

batch of 25% of the total number of samples will be tested. If all samples tested are below the limit of quantification of the assay, further analyses will not be undertaken until the sensitivity of the assay is significantly increased.

10.3 Adverse event monitoring

Subjects will be asked by direct questioning at each visit whether they have experienced any AEs. Aes will be assessed as described in Section 12.2.

10.4 Concomitant medications

Changes in use or new medications used during course of study will be documented and reviewed at each study visit.

10.5 Efficacy assessments

10.5.1 Pain intensity

10.5.1.1 NPRS

The NPRS is an 11 point scale which grades pain from 0 (no pain) to 10 (worst pain imaginable). It is a recommended core outcome for the assessment of pain intensity in clinical trials of chronic pain treatments.¹⁶

Subjects will be asked to rate the intensity of their average pain over the previous 24 hours in a diary. Entries should be made at the same time each evening.

10.5.2 Patient reported outcomes

10.5.2.1 Short form BPI

The interference scale of the short form BPI¹⁵ has been recommended by international consensus¹⁶ as a core outcome measure of physical functioning in chronic pain clinical trials. It measures the interference of pain on seven items (general activity, mood, walking ability, work, relations with other people, sleep, enjoyment of life). Each scale is graded from 0 (does not interfere) to 10 (completely interferes). The result is the mean of the scores from the seven items.

10.5.2.2 SF-MPQ-2

The SF-MPQ-2¹⁷ is a measure of both neuropathic and non-neuropathic pain, modified from the commonly used McGill Pain Questionnaire¹⁸ and Short-form McGill Pain Questionnaire.¹⁹ The SF-MPQ-2 adds seven symptoms characteristic of neuropathic pain to the SF-MPQ and has response scales from 0 to 10.

10.5.2.3 NPSI

The NPSI was designed specifically for the assessment of the different symptoms of neuropathic pain.²⁰ It contains ten items related to different pain descriptors (e.g. burning, squeezing, electric-shock, stabbing, tingling), allowing the assessment of the different dimensions of neuropathic pain, and two items on frequency and duration of pain. Each pain descriptor is rated on an 11-point numeric rating scale from 0 (no pain) to 10 (worst imaginable pain). Total pain intensity score is calculated by the sum of the 10 descriptors.

